6.4. Rescue Medications & Supportive Care

Participants should receive appropriate supportive care measures as deemed necessary by the treating investigator. Suggested supportive care measures for the management of AEs with potential immunologic etiology are outlined along with the dose modification guidelines in Section 6.3 [Table 3]. Where appropriate, these guidelines include the use of oral or IV treatment with corticosteroids, as well as additional anti-inflammatory agents if symptoms do not improve with administration of corticosteroids. Note that several courses of steroid tapering may be necessary as symptoms may worsen when the steroid dose is decreased. For each is order, attempts should be made to rule out other causes such as metastatic disease or bacterial or viral infection, which might require additional supportive care. The treatment guidelines are intended to be applied when the Investigator determines the events to be related to pembrolizumab, and/or SurVaxM.

Note: If after the evaluation of the event, it is determined not to be related to pembrolizumab, the Investigator does not need to follow the treatment guidance. Refer to [Table 3] in Section 6.3 for guidelines regarding dose modification and supportive care.

It may be necessary to perform conditional procedures such as bronchoscopy, endoscopy, or skin photography as part of evaluation of the event.

6.5 Criteria for Removal from Study

Participants may discontinue study treatment at any time for any reason or be dropped from the study treatment at the discretion of the investigator should any untoward effect occur. In addition, a participant may be discontinued from study treatment by the investigator or the Sponsor if study treatment is inappropriate, the trial plan is violated, or for administrative and/or other safety reasons. Specific details regarding procedures to be performed at study treatment discontinuation are provided in Section 8.0. – Other Procedures.

A participant must be discontinued from study treatment but continue to be monitored in the study for any of the following reasons:

- The participant or participant's legally acceptable representative requests to discontinue study treatment.
- Confirmed radiographic disease progression
- Any progression or recurrence of any malignancy, or any occurrence of another malignancy that requires active treatment
- Unacceptable adverse experiences as described in Section 6.3
- The participant has a medical condition or personal circumstance which, in the opinion of the investigator and/or sponsor, places the participant at unnecessary risk from continued administration of study treatment.

Version 9: 1-Nov-2017

- The participant has a confirmed positive serum pregnancy test
- Noncompliance with study treatment or procedure requirements
- Recurrent Grade 2 pneumonitis
- The participant is lost to follow-up

Note: The number of treatments is calculated starting with the first dose.

- Administrative reasons
- Completion of pembrolizumab Q3W monotherapy consists of 35 treatments (approximately 2 years

6.5.1 Clinical Criteria for Early Trial Termination

Early trial termination will be the result of the criteria specified below:

- 1. Quality or quantity of data recording is inaccurate or incomplete
- 2. Poor adherence to protocol and regulatory requirements
- 3. Incidence or severity of adverse drug reaction in this or other studies indicates a potential health hazard to participants
- 4. Plans to modify or discontinue the development of the study drug

In the event of Merck decision to no longer supply study drug, ample notification will be provided so that appropriate adjustments to participant treatment can be made.

6.6 **Duration of Follow-Up**

Post treatment follow up (F/U) visits will be done at 30 days post treatment. To capture all possibly delayed immune-related adverse events (irAEs), the safety follow-up period will be at least 90 days for all patients receiving, regardless of initiation of subsequent anticancer therapy.

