Pregnancies and infant exposures during breastfeeding that occur from the time of treatment through 120 days following cessation of Sponsor's product, or 30 days following cessation of treatment if the participant initiates new anticancer therapy, whichever is earlier, must be reported by the investigator. All reported pregnancies must be followed to the completion/termination of the pregnancy. Pregnancy outcomes of spontaneous abortion, missed abortion, benign hydatidiform mole, blighted ovum, fetal death, intrauterine death, miscarriage and stillbirth must be reported as serious events (Important Medical Events). If the pregnancy continues to term, the outcome (health of infant) must also be reported.

Such events must be reported within 24 hours to the Sponsor and within 2 working days to Merck Global Safety. (Attn: Worldwide Product Safety; [contact])

Version 9: 1-Nov-2017

Events of Clinical Interest

Selected non-serious and serious adverse events are also known as Events of Clinical Interest (ECI) and must be reported within 2 working days to Merck Global Safety. (Attn: Worldwide Product Safety; [contact]).

For the time period beginning when the consent form is signed until treatment allocation, any ECI, or follow up to an ECI, that occurs to any participant must be reported within 2 working days to Merck Global Safety if it causes the participant to be excluded from the trial, or is the result of a protocol-specified intervention, including but not limited to washout or discontinuation of usual therapy, diet, placebo treatment or a procedure.

For the time period beginning at treatment allocation through 90 days following cessation of treatment, or 30 days following cessation of treatment if the participant initiates new anticancer therapy, whichever is earlier, any ECI, or follow up to an ECI, whether or not related to Merck product, must be reported within 2 working days to Merck Global Safety.

Events of clinical interest for this trial include:

- 1. an overdose of Merck product Definition of an Overdose for This Protocol and Reporting of Overdose to the Sponsor, that is not associated with clinical symptoms or abnormal laboratory results.

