6.2.2. Acceptable Concomitant Medications

All treatments that the investigator considers necessary for a participant's welfare may be administered at the discretion of the investigator in keeping with the community standards of medical care. All concomitant medication will be recorded on the case report form (CRF) including all prescription, over-the-counter (OTC), herbal supplements, and IV medications and fluids. If changes occur during the trial period, documentation of drug dosage, frequency, route, and date may also be included on the CRF.

Version 9: 1-Nov-2017

All concomitant medications received within 28 days before the first dose of trial treatment and 30 days after the last dose of trial treatment should be recorded. Concomitant medications administered after 30 days after the last dose of trial treatment should be recorded for SAEs and ECIs.

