6.6.1 Safety Follow-Up Visit

The mandatory Safety Follow-Up Visit should be conducted approximately 30 days after the last dose of study treatment or before the initiation of a new anti-cancer treatment, whichever comes first. All AEs that occur prior to the Safety Follow-Up Visit should be recorded. Participants with an AE of Grade > 1 will be followed until the resolution of the AE to Grade 0-1 or until the beginning of a new anti-cancer therapy, whichever occurs first. SAEs that occur within 90 days of the end of treatment or before initiation of a new anti-cancer treatment should also be followed and recorded.

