8.0 ADVERSE EVENTS AND POTENTIAL RISKS

8.0.1 Assessing and Recording Adverse Events

An adverse event is defined as any untoward medical occurrence in a patient or clinical investigation participant administered a pharmaceutical product and which does not necessarily have to have a causal relationship with this treatment. An adverse event can therefore be any unfavorable and unintended sign (including an abnormal laboratory finding, for example), symptom, or disease temporally associated with the use of a medicinal product or protocol-specified procedure, whether or not considered related to the medicinal product or protocol-specified procedure. Any worsening (i.e., any clinically significant adverse change in frequency

Version 9: 1-Nov-2017

and/or intensity) of a preexisting condition that is temporally associated with the use of the Merck's product, is also an adverse event.

Changes resulting from normal growth and development that do not vary significantly in frequency or severity from expected levels are not to be considered adverse events. Examples of this may include, but are not limited to, teething, typical crying in infants and children and onset of menses or menopause occurring at a physiologically appropriate time.

Merck product includes any pharmaceutical product, biological product, device, diagnostic agent or protocol-specified procedure, whether investigational (including placebo or active comparator medication) or marketed, manufactured by, licensed by, provided by or distributed by Merck for human use.

Adverse events may occur during the course of the use of Merck product in clinical trials, or as prescribed in clinical practice, from overdose (whether accidental or intentional), from abuse and from withdrawal.

All AEs, SAEs and other reportable safety events that occur after the consent form is signed but before treatment allocation must be reported by the investigator if the participant is receiving placebo run-in or other run-in treatment, if the event cause the participant to be excluded from the study, or is the result of a protocol-specified intervention, including but not limited to washout or discontinuation of usual therapy, diet, or a procedure.

- All AEs from the time of treatment allocation through 30 days following cessation of study treatment must be reported by the investigator.

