- All AEs meeting serious criteria, from the time of treatment allocation through 90 days following cessation of study treatment, or 30 days following cessation of study treatment if the participant initiates new anticancer therapy, whichever is earlier must be reported by the investigator.
- All pregnancies and exposure during breastfeeding, from the time of treatment allocation through 120 days following cessation of study treatment, or 30 days following cessation of study treatment if the participant initiates new anticancer therapy must be reported by the investigator.
- Additionally, any SAE brought to the attention of an investigator at any time outside of the time period specified above must be reported immediately by the investigator if the event is considered to be drug-related.

Investigators are not obligated to actively seek AE or SAE or other reportable safety events in former study participants. However, if the investigator learns of any SAE, including a death, at any time after a participant has been discharged from the study, and he/she considers the event to be reasonably related to the study treatment or study participation, the investigator must promptly notify Merck.

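### Section 6.6 promises at least 90 days of follow-up for all delayed immune-related events, but the recording rules stop at about day 30 for non-serious ones and the new-therapy cut-offs disagree

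*Combined protocol and SAP*

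**What the plan says.** Section 6.6 (Duration of Follow-Up) gives an aim and a period: "To capture all possibly delayed immune-related adverse events (irAEs), the safety follow-up period will be at least 90 days for all patients receiving". It also gives a scope, since the period is to run "regardless of initiation of subsequent anticancer therapy". Section 6.3 gives the reason: immune-related adverse events (irAEs) can first appear months after dosing has ended.

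Other sections then tell sites what to collect.

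- Section 8.0.1, all adverse events: "All AEs from the time of treatment allocation through 30 days following cessation of study treatment must be reported by the investigator".
- Section 8.0.1, serious adverse events (SAEs): 90 days, "or 30 days following cessation of study treatment if the participant initiates new anticancer therapy, whichever is earlier must be reported by the investigator". An SAE judged drug-related stays reportable whenever the investigator hears of it.
- Section 6.6.1 sets a mandatory visit about 30 days after the last dose, brought forward if a new anticancer treatment starts sooner. "All AEs that occur prior to the Safety Follow-Up Visit should be recorded". Beyond that visit it names only "SAEs that occur within 90 days of the end of treatment or before initiation of a new anti-cancer treatment".
- Section 6.2.2, medications: "Concomitant medications administered after 30 days after the last dose of trial treatment should be recorded for SAEs and ECIs".
- The ECI rule in Section 1.3: 90 days, "or 30 days following cessation of treatment if the participant initiates new anticancer therapy, whichever is earlier, any ECI". The ECI list has two entries, an overdose without symptoms and a defined combination of abnormal liver tests.
- Section 8.3 repeats, for SAE reports to the sponsor and the pembrolizumab supplier, the 90-day window with the same 30-day cut.

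**The concern.** Safety and tolerability is the first secondary objective (Section 2.2), and Section 1.4 notes that few trials have yet combined pembrolizumab with a specific cancer vaccine. The late irAE profile is part of what this study is meant to describe.

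Sites tend to work from the recording and reporting sections. A site that follows Sections 8.0.1, 6.6.1 and 6.2.2 to the letter would not collect everything that Section 6.6 says will be captured. A report could then describe at least 90 days of safety follow-up when its data on new non-serious events end at about day 30. A lack of late events would look like evidence when it was only a lack of collection. For patients who move to new therapy, sites could defend different stopping points, so follow-up would be uneven from patient to patient.

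**Working it through.** The plan states no figure to reproduce, and the check needs only day counts. Days run from the last dose or the end of treatment; the sections use both as their starting point.

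| Rule | Covers | Ends, no new therapy | Ends, new therapy started |
|---|---|---|---|
| 6.6 | all delayed irAEs | day 90 at least | day 90 at least |
| 6.6.1 | all AEs | visit at about day 30 | visit moved ahead of the new therapy, if sooner |
| 6.6.1 | SAEs | day 90 | start of new therapy |
| 8.0.1 | all AEs | day 30 | day 30 |
| 8.0.1 and 8.3 | SAEs | day 90 | day 30 |
| ECI rule, 1.3 | two listed ECIs | day 90 | day 30 |
| 6.2.2 | medications | day 30, then only for SAEs and ECIs | no separate clause |

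The 6.6.1 entry for SAEs under new therapy reads its alternative as a stop, in line with the rest of that section.

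**Case 1: non-serious Grade 2 pneumonitis starting on day 45, no new therapy.**
- Section 6.6: inside, since 45 is below 90.
- Section 8.0.1, all AEs: outside, since 45 is above 30.
- Section 6.6.1: outside, because the visit has passed and the event is not serious.
- ECI rule: outside, because it is neither an overdose nor the liver-test pattern.
- Section 6.2.2: the corticosteroids that Table 3 directs need not be recorded.

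The same holds for any new-onset, non-serious, non-ECI irAE on days 31 to 90, a span of 90 − 30 = 60 days.

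**Case 2: the listed liver-test pattern, non-serious, on day 40, after new therapy on day 20.**
- Section 6.6: inside, because new therapy makes no difference there.
- ECI rule: outside, because the window has been cut to day 30.
- Section 8.0.1, all AEs: outside.
- Section 6.6.1: outside, because the visit was due before day 20.

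**Case 3: a non-serious AE on day 25, after new therapy on day 20.**
- Section 8.0.1 requires it, since 25 is below 30.
- Section 6.6.1 does not, because its visit was due before day 20.

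So the two general recording rules also disagree with each other, quite apart from Section 6.6.

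**Case 4: an SAE of possible immune origin on day 40, with new therapy on day 60.**
- Sections 6.6 and 6.6.1 cover it.
- Sections 8.0.1 and 8.3, read literally, cut the window to day 30 and do not, unless the event is judged drug-related.

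**The case against.** The best defence is that Section 6.6 is itself a rule. On that reading Section 8.0.1 sets a minimum for adverse events in general, and Section 6.6 adds a specific requirement for irAEs. In addition, the split between 30 days for AEs and 90 days for SAEs, with the same shortening for new therapy, is the one used in the pembrolizumab reference safety dataset described in Section 1.2. Keeping it makes AE and SAE collection comparable with those data. The gap is also narrow: SAEs, drug-related SAEs at any time, ECIs, and AEs above Grade 1 already on record (followed to resolution or new therapy) all have a route.

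Much of this stands. A reader might infer that late non-serious irAEs have no basis for collection anywhere. The documents do not support that, because Section 6.6 plainly intends to capture them; the fault is contradiction. The reference dataset is also a good reason to leave the expedited-reporting windows alone.

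It does not reconcile the text. Section 6.6 refers to all delayed irAEs and disregards new therapy, and the SAE rule does neither. Section 6.6 names no recording step after its day-30 visit, while Sections 6.6.1 and 6.2.2 say what is to be recorded and stop short. If Section 6.6 prevails, those sections need amending to agree with it.

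**Conclusion.** The contradiction holds on the protocol's own wording. A new-onset, non-serious, non-ECI irAE on days 31 to 90 falls within Section 6.6 and outside the recording rules in Sections 8.0.1, 6.6.1 and 6.2.2. The new-therapy clauses give three different answers: no cut-off (6.6), the start of new therapy (6.6.1), and day 30 (8.0.1 for SAEs, 8.3 and the ECI rule).

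Its size in events is unknown. A reader might treat the share of uncovered days, the remaining drug level, or the design PFS6 rates as a measure of loss. None of them serves. The documents give no rate for delayed non-serious irAEs, do not link drug level to their onset, and do not say how many patients start new therapy within 90 days of the last dose. Nor is there any effect on PFS6 or power.

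The conclusion assumes that sites apply the recording sections as written and that Section 6.6 states the intended standard. The point merits an amendment because it bears on the first secondary objective and is cheap to correct.

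**What to change.** 1. In Sections 8.0.1 and 6.6.1, require every irAE of any grade, serious or not, to be recorded on the case report form through 90 days after the last dose, regardless of new therapy. In Section 6.2.2, extend medication recording to drugs given for those events.
2. In Sections 8.0.1 and 8.3 and in the ECI rule, state that the 30-day new-therapy cut applies to expedited reporting and does not shorten this irAE recording.
3. Add an irAE question to the 8-week follow-up visit (6.6.2) and the 12-week survival call (6.6.3). Have the first contact on or after day 90 ask about the whole interval up to day 90.

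The last item is needed because the existing contacts can fall short. The first 8-week visit after day 30 is at 30 + 56 = day 86, or days 79 to 93 with the ±7-day allowance. A 12-week call is at day 84 if counted from the last dose; the protocol does not give its starting point. The next contacts would be at 86 + 56 = day 142 or 84 + 84 = day 168.

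The cost is a short amendment and slightly more data collection, with some reliance on recall when the closing contact comes well after day 90. No new visit has to be added. Recording irAEs without classing them as ECIs avoids extending the two-working-day report to them.

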6.6.1 Safety Follow-Up Visit

The mandatory Safety Follow-Up Visit should be conducted approximately 30 days after the last dose of study treatment or before the initiation of a new anti-cancer treatment, whichever comes first. All AEs that occur prior to the Safety Follow-Up Visit should be recorded. Participants with an AE of Grade > 1 will be followed until the resolution of the AE to Grade 0-1 or until the beginning of a new anti-cancer therapy, whichever occurs first. SAEs that occur within 90 days of the end of treatment or before initiation of a new anti-cancer treatment should also be followed and recorded.

6.6.2 Follow-up Visits

Participants who discontinue study treatment for a reason other than disease progression will move into the Follow-Up Phase and should be assessed every 8 weeks (\pm 7 days) by radiologic imaging to monitor disease status. Every effort should be made to collect information regarding disease status until the start of new anti-cancer therapy, disease progression, death, end of the study or if the participant begins retreatment with pembrolizumab as detailed in Section 6.3.1. Information regarding post-study anti-cancer treatment will be collected if new treatment is initiated.

Participants who are eligible to receive retreatment with pembrolizumab according to the criteria in Section 6.3.1.

6.6.3 Survival Follow-up

Participants who experience confirmed disease progression or start a new anticancer therapy, will move into the Survival Follow-Up Phase and should be contacted by telephone every 12 weeks to assess for survival status until death, withdrawal of consent, or the end of the trial, whichever occurs first.

7.0 DOSE DELAYS / DOSE MODIFICATIONS

AEs associated with pembrolizumab exposure may represent an immunologic etiology. These immune-related AEs (irAEs) may occur shortly after the first dose or several months after the last dose of pembrolizumab treatment and may affect more than on body system simultaneously. Therefore, early recognition and initiation of treatment is critical to reduce complications. Based on existing clinical study data, most irAEs were reversible and could be managed with interruptions of pembrolizumab, administration of corticosteroids and/or other supportive care. For suspected irAEs, ensure adequate evaluation to confirm etiology or exclude other causes. Additional procedures or tests such as bronchoscopy, endoscopy, skin biopsy may be included as part of the evaluation. Based on the severity of irAEs, withhold or permanently discontinue pembrolizumab and administer corticosteroids. Dose modification and toxicity management guidelines for irAEs associated with pembrolizumab.

8.0 ADVERSE EVENTS AND POTENTIAL RISKS

8.0.1 Assessing and Recording Adverse Events

An adverse event is defined as any untoward medical occurrence in a patient or clinical investigation participant administered a pharmaceutical product and which does not necessarily have to have a causal relationship with this treatment. An adverse event can therefore be any unfavorable and unintended sign (including an abnormal laboratory finding, for example), symptom, or disease temporally associated with the use of a medicinal product or protocol-specified procedure, whether or not considered related to the medicinal product or protocol-specified procedure. Any worsening (i.e., any clinically significant adverse change in frequency

Version 9: 1-Nov-2017

and/or intensity) of a preexisting condition that is temporally associated with the use of the Merck's product, is also an adverse event.

Changes resulting from normal growth and development that do not vary significantly in frequency or severity from expected levels are not to be considered adverse events. Examples of this may include, but are not limited to, teething, typical crying in infants and children and onset of menses or menopause occurring at a physiologically appropriate time.

Merck product includes any pharmaceutical product, biological product, device, diagnostic agent or protocol-specified procedure, whether investigational (including placebo or active comparator medication) or marketed, manufactured by, licensed by, provided by or distributed by Merck for human use.

Adverse events may occur during the course of the use of Merck product in clinical trials, or as prescribed in clinical practice, from overdose (whether accidental or intentional), from abuse and from withdrawal.

All AEs, SAEs and other reportable safety events that occur after the consent form is signed but before treatment allocation must be reported by the investigator if the participant is receiving placebo run-in or other run-in treatment, if the event cause the participant to be excluded from the study, or is the result of a protocol-specified intervention, including but not limited to washout or discontinuation of usual therapy, diet, or a procedure.

- All AEs from the time of treatment allocation through 30 days following cessation of study treatment must be reported by the investigator.
- All AEs meeting serious criteria, from the time of treatment allocation through 90 days following cessation of study treatment, or 30 days following cessation of study treatment if the participant initiates new anticancer therapy, whichever is earlier must be reported by the investigator.
- All pregnancies and exposure during breastfeeding, from the time of treatment allocation through 120 days following cessation of study treatment, or 30 days following cessation of study treatment if the participant initiates new anticancer therapy must be reported by the investigator.
- Additionally, any SAE brought to the attention of an investigator at any time outside of the time period specified above must be reported immediately by the investigator if the event is considered to be drug-related.

Investigators are not obligated to actively seek AE or SAE or other reportable safety events in former study participants. However, if the investigator learns of any SAE, including a death, at any time after a participant has been discharged from the study, and he/she considers the event to be reasonably related to the study treatment or study participation, the investigator must promptly notify Merck.

